1 PROTOCOL SUMMARY

1.1 Synopsis

Short Title:

An *In Situ* Erosion Study to Investigate the Efficacy of an Experimental Dentifrice to Remineralize Enamel.

Background and Rationale:

This study will investigate the ability of an experimental dentifrice containing 1150ppm fluoride to remineralize acid-softened dental enamel and help prevent further demineralization compared to a 0ppm fluoride placebo dentifrice and a marketed, fluoride-containing dentifrice (Reference Dentifrice). The study will utilize an established *in situ* model where partially demineralized enamel specimens will be placed in a dental palatal appliance, treated intra orally then allowed to remineralize *in situ* for 4 and 12 hours. Efficacy will be evaluated through laboratory measurement of the surface microhardness recovery (SMHR), relative erosion resistance (RER), acid resistance ratio (ARR) and the enamel fluoride uptake (EFU).

Objectives and Endpoints:

Objectives	Endpoints
Primary	
To investigate the efficacy of an experimental dentifrice containing 1150 ppm fluoride and 5% KNO ₃ to enhance remineralization of enamel compared to a placebo dentifrice (0ppm fluoride) after 4 hours of intra-oral exposure.	%SMHR at 4 hrs.
Secondary	
To investigate the efficacy of an experimental dentifrice containing 1150 ppm fluoride and 5% KNO ₃ to inhibit demineralization of enamel compared to a placebo dentifrice (0ppm fluoride) after 4 hours of intra-oral exposure.	%RER at 4 hrs.
To investigate the efficacy of an experimental dentifrice containing 1150 ppm fluoride and 5% KNO ₃ to enhance remineralization of enamel compared to a marketed, reference dentifrice containing 1100ppm fluoride after 4 hours of intra-oral exposure.	%SMHR at 4 hrs.
To investigate the efficacy of an experimental dentifrice containing 1150 ppm fluoride and 5% KNO ₃ to enhance remineralization of enamel compared to a placebo dentifrice (0ppm fluoride) and a marketed, reference dentifrice containing 1100ppm fluoride after 12 hours of intra-oral exposure.	%SMHR at 12 hrs.
To investigate the efficacy of an experimental dentifrice containing 1150 ppm fluoride and 5% KNO ₃ to inhibit demineralization of enamel compared to a reference dentifrice containing 1100ppm fluoride after 4 hours of intra-oral exposure.	%RER at 4 hrs.
To investigate the efficacy of an experimental dentifrice containing 1150 ppm fluoride and 5% KNO ₃ to inhibit demineralization of enamel compared to a placebo dentifrice (0ppm fluoride) and a marketed, reference dentifrice containing 1100ppm fluoride after 12 hours of intra-oral exposure.	%RER 12 hrs.
To investigate the efficacy of an experimental dentifrice containing 1150 ppm fluoride and 5% KNO ₃ to promote fluoride uptake in enamel compared to a placebo dentifrice (0ppm fluoride) and a marketed, reference dentifrice containing 1100ppm fluoride after 4 and 12 hours of intra-oral exposure.	EFU at 4 and 12 hrs.

Property of Haleon- Confidential

May not be used, divulged, published or otherwise disclosed without the consent of Haleon

To investigate the efficacy of an experimental dentifrice containing 1150 ppm fluoride and 5% KNO ₃ to reduce future acid-induced demineralization in enamel compared to a placebo dentifrice (0ppm fluoride) and a marketed, reference dentifrice containing 1100ppm fluoride after 4 and 12 hours of intra-oral exposure.	ARR at 4 and 12 hrs.
To investigate the efficacy of a marketed, reference dentifrice containing 1100ppm fluoride, to enhance remineralization, inhibit demineralization, to reduce future acid-induced demineralization and to promote fluoride uptake in enamel compared to a placebo dentifrice (0ppm fluoride) after 4 and 12 hours of intra-oral exposure.	%SMHR, %RER, EFU, ARR at 4 and 12 hrs.
Exploratory	
To calculate the proportion of subjects who evidence a RER ratio (%RER 0ppm fluoride placebo and 5% KNO ₃ : %RER experimental dentifrice containing 1150 ppm fluoride) ≥ 3 and ≥ 2.5	%RER at 4 and 12 hrs.
Safety	
To assess the oral tolerability of an experimental dentifrice containing 1150ppm fluoride and 5% KNO ₃ .	Treatment emergent adverse events

Abbreviations: SMHR: Surface micro hardness recovery, RER: Relative erosion resistance, EFU: Enamel fluoride uptake, ARR: Acid resistance ratio, KNO₃: potassium nitrate.

Study Design:

This will be a randomized, controlled, single center, single- blind (to the dental examiner and specimen analysts), 3 period, 3 treatment, cross-over, *in situ* design. Previously demineralized bovine enamel specimens will be placed intra orally using a palatal appliance and the remineralizing performance of the experimental, reference and placebo dentifrices evaluated at 4 and 12 hours post toothbrushing, based on surface micro hardness measurements of the bovine enamel specimens. This study will be carried out in healthy adults with a maxillary dental arch suitable for the retention of the palatal appliance. Subjects will be recruited from an existing panel of subjects pre-fitted with a palatal appliance.

In this study there will be 7 visits, 1 screening visit to assess subject eligibility, 3 treatment visits, where the study dentifrices will be dispensed and used under the supervision of a suitably trained study site personnel, and 3 follow up visits to perform an OST examination, assess for Adverse Events and allow the subject to return their palatal appliance. Sufficient subjects will be screened to randomize up to 33 subjects to study treatment to ensure at least 30 subjects complete the study. At screening (Visit 1), subjects will give their written informed consent to participate in the study. Demography, relevant medical history and current medications/treatments will be recorded, followed by oral soft tissue (OST) and oral hard tissue (OHT) examinations. Subjects will then have their stimulated and unstimulated salivary flow rates measured and subjects meeting the relevant study inclusion/exclusion criteria will try-in their palatal appliance and be considered eligible to enroll in the study. Enrolled subjects will then be dispensed the wash-out dentifrice, toothbrush and diary.

Prior to each treatment visit, there will be a washout period of a minimum of 3 days. During this period subjects will use their own dentifrice and toothbrush for at least one day, and a 0ppm fluoride washout dentifrice and study toothbrush (provided) for two days immediately prior to the next scheduled visit (including on the morning of the scheduled visit).

At treatment visits (Visits 2, 4 & 6), subjects will provide details of their concomitant medications and undergo an OST examination. Subject's diaries will be reviewed to ensure compliance with the use of the wash-out dentifrice. Subjects deemed suitable to continue in the study will be randomized to the order of treatments (Visit 2 only) and wear an oral palatal

Property of Haleon- Confidential

May not be used, divulged, published or otherwise disclosed without the consent of Haleon

appliance holding 8 bovine enamel specimens. Details of enamel specimen preparation will be specified in the Laboratory Procedures Document. The palatal appliances will be specifically made for each eligible subject, and each will carry two plastic holders containing a total of eight bovine enamel specimens (four in each holder). Once the appliance is fitted in the mouth, a five minute equilibration period will ensue following which each subject will brush their teeth with their assigned product, one product per treatment visit as described below.

Under supervision while the intraoral appliance is in place, the subjects will brush the buccal surfaces of their natural teeth using 1.5 ± 0.1 g of dentifrice and a soft toothbrush for 25 seconds to create a slurry. Subjects will be instructed not to expectorate the slurry and will then swish the slurry around their mouth for 95 seconds to permit direct contact of the dentifrice slurry with the enamel specimens. After expectorating the slurry, the subjects will gently rinse their mouths with 15 mL of tap water for 10 seconds before expectorating again. The toothbrush, however, will not come into contact with the enamel specimens or the appliance as this could cause abrasion of the enamel specimens.

Subjects will then remain at the study site for 4 hours post toothbrushing when their appliance will be removed (at $4\text{hrs} \pm 10$ mins post toothbrushing) and 4 designated enamel specimens will be withdrawn from the appliance. Subjects will then be served an optional lunch which will be consumed within a 30 ± 10 minute time period. The subjects will then brush and rinse their mouth with water, after which they will have their appliance reinserted and be allowed to leave the site. Subjects will be reminded to not eat or drink (except for water) while wearing their appliance.

Subjects will be given verbal and written home instructions/diary which will instruct them to remove their appliance at 8.5 hours following the toothbrushing. The time for removal will be detailed on the instruction/diary sheet. They will be allowed to eat a meal of their choice over a 30 ± 10 minute timed period, brush their teeth and rinse their mouth with water and refit their appliance after the 30 ± 10 minute timed period is up. After 13 ± 0.5 hours following the initial brushing time, the subject will be instructed to remove their appliance, rinse it under running water and store moist in the supplied container in their refrigerator overnight. The time for this removal will also be given on their instruction/diary sheet. In addition, a member of the study team will give a reminder call to the subject prior to the completion of the 12 hour intraoral exposure. Subjects will then attend a follow-up visit (Visits 3, 5 and 7) the following day to return their appliance to the site and to receive an OST examination to evaluate any potential oral AEs. At Visit 6 only, the subjects will return their washout dentifrice and at the final post treatment visit (Visit 7) the subject will also receive an OHT exam and end of study documentation will be completed.

The enamel specimens will be evaluated both prior to and after intra-oral exposure. Surface microhardness (SMH) will be used to evaluate changes in the mineral content of enamel and is used to calculate surface micro hardness recovery (%SMHR), relative erosion resistance (%RER) and acid resistance ratio (ARR). The incorporation of fluoride into the enamel specimens will be assessed by enamel fluoride uptake (EFU) measurements. For each treatment and subject, these measurements will be performed on the same enamel specimen as described in the Laboratory Procedure Document, in the four enamel specimens removed at each time point. The erosive acid challenges, with a commercially available grapefruit juice, will be carried out *ex vivo* and therefore does not pose a risk to the subject's teeth.

AEs and medical device incidents will be monitored through out the study and recorded at every site visit following signing of informed consent.

Study Products:

Test Dentifrice	Placebo Control	Reference Dentifrice
Experimental Dentifrice containing 1150ppm fluoride and 5% KNO ₃ *	0ppm fluoride dentifrice containing 5% KNO ₃	Crest Pro-Health Densify Daily Protection

* KNO₃ is commonly used in other marketed anti sensitive toothpaste.

All dentifrices will be applied in the same manner by brushing 1.5±0.1g of dentifrice on to the buccal surfaces of their natural teeth for 25 timed seconds and then swishing the resulting dentifrice slurry around the mouth, without further brushing, for a timed period of 95 seconds.

Subjects will use a 0ppm fluoride washout dentifrice twice daily for 2 days prior to each treatment visit in place of their usual oral hygiene practice.

Type and Planned Number of Subjects:

Study subjects of either sex and any gender, aged 18-65 years, who are in good general health and a maxillary dental arch suitable for the retention of the palatal appliance.

Sufficient subjects will be screened to randomize up to 33 subjects to study treatment to ensure at least 30 evaluable subjects complete all periods of the study.

Statistical Analysis:

The %SMHR, %RER and ARR at the subject visit level (to be used in the analysis) will be derived as the mean of the specimen means (across replicates within a specimen) within that visit.

The mean EFU across specimens relating to a specific timepoint (4 or 12 hours) will be derived to represent the visit level EFU at the timepoint to be used in the analysis.

A separate mixed model (including results across all 3 study products) will be used to analyze each parameter at each timepoint (4 or 12 hours) with fixed effects for treatment and study visit, as well as random effect for subject. Kenward Rogers degrees of freedom approach will be applied. The least square means for each study product will be presented along with the 3 pairwise differences of interest between least square means (including two-sided p-value and 95% confidence interval) to test for a difference between products.

Statistical testing of all endpoints in this study will be conducted at a two-sided significance level of 0.05. A sequential testing strategy will be applied to preserve the overall type-1 error control for the respective sequential comparisons between the Experimental dentifrice and Placebo Control at 12 hours for the %SMHR (primary endpoint) and %RER (secondary endpoint). There will be no further adjustments for multiplicity.

1.2 Schedule of Activities

The schedule of activities table provides an overview of the subject visits and study procedures.

The investigator may schedule visits (unplanned visits) in addition to those listed on the schedule of activities, to conduct evaluations or assessments required to protect the well-being of the subject.

Procedure/Assessment	Screening	Study Period 1		Study Period 2		Study Period 3	
	Visit 1	Visit 2 (Treatment)	Visit 3 (V2+1day)	Visit 4 (Treatment)	Visit 5 (V4+1day)	Visit 6 (Treatment)	Visit 7 (V6+1day)
Informed consent	X						
Demographics	X						
Medical history	X						
Current/prior/concomitant medication review	X	X	X	X	X	X	X
OST Examination ¹	X	X	X	X	X	X	X
OHT Examination	X						X
Assessment of stimulated and unstimulated saliva flow rate ²	X						
Review of inclusion/exclusion criteria	X						
Try-in of palatal appliance	X						
Subject eligibility	X						
Dispense wash-out products and diary	X						
Diary review		X	X	X	X	X	X
Subject continuance		X	X	X	X	X	X
Randomization to treatment sequence		X					
Place palatal appliance fitted with enamel specimens into subject's mouth ³		X		X		X	
Supervised toothbrushing		X		X		X	
Intra oral phase 4 hours ^{3,4}		X		X		X	

Property of Haleon- Confidential

May not be used, divulged, published or otherwise disclosed without the consent of Haleon

Procedure/Assessment	Screening		Study Period 1		Study Period 2		Study Period 3	
	Visit 1		Visit 2 (Treatment)	Visit 3 (V2+1day)	Visit 4 (Treatment)	Visit 5 (V4+1day)	Visit 6 (Treatment)	Visit 7 (V6+1day)
Intra oral phase 12 hours ^{3,5}			X		X		X	
Adverse events review ⁶	X		X	X	X	X	X	X
Medical device incidents review ¹			X	X	X	X	X	X
Return wash-out products							X	
Return palatal appliance				X		X		X
Study conclusion								X

Abbreviations: OST: Oral Soft Tissue, OHT: Oral Hard Tissue.

Footnotes:

1. At Visits 2, 4 & 6 OST examination will be performed prior to insertion of the appliance and at Visits 3, 5 & 7 when the subject returns their palatal appliance.
2. Re-evaluation of saliva flow may be required within the study should the subject begin a treatment of medications likely to induce xerostomia.
3. Laboratory analysis of enamel specimens performed prior to placing and after removing the specimens from the palatal appliance as described in the separate laboratory procedures document.
4. Four enamel specimens will be removed from the palatal appliance after wearing the appliance for 4 hours \pm 10 min after toothbrushing. Subject will be offered lunch to be eaten over a 30 \pm 10 minute period and then be allowed to leave the site with instructions on how and when to eat dinner (30 \pm 10 minute period between hours 8.5 and 9), and remove (hour 13), store and return their appliance.
5. Subjects will remove their appliance after 12 hours \pm 30 mins of wearing post toothbrushing (13 \pm 0.5 hours since brushing with product). Subjects will then rinse and store the appliance as instructed by the site staff. Subjects will return the appliance to the study site the following day. The study site staff will recover the 4 remaining enamel sections, then the appliance will be cleaned, disinfected and stored at site until the next treatment visit.
6. Adverse Events (AEs), Serious Adverse Events (SAEs) and medical device incidents collected from immediately after subject provides consent to participate in the study by the completion of the Informed Consent Form (ICF). Medical device in this study is the supplied toothbrush.

Property of Haleon- Confidential

May not be used, divulged, published or otherwise disclosed without the consent of Haleon

2 INTRODUCTION

Dental erosion is the irreversible loss of tooth substance by chemical processes not involving bacteria. It is a cyclical process, influenced by demineralization and remineralization. Demineralization of the enamel surface can occur by the exposure to acids either from internal origin, such as gastric acids from refluxes, and or external from dietary sources; if of sufficient frequency and severity. The erosive challenges *in vivo* are brief and it's unlikely they are a major cause of surface loss when occurring on their own ([Shellis et al., 2011](#)), but this softening of the hard tissues surface makes it more susceptible to further physical wear from abrasion (tooth brushing) and attrition (grinding) resulting in tissue loss. The process of demineralization cycles with remineralization, which is the process of placing minerals back into the previously demineralized hard tissue by the ionic constituents of saliva, ideally to achieve mineral that is more resistant to subsequent demineralization ([Cochrane et al., 2012](#)).

It is well accepted that fluoride containing dentifrices should be part of an appropriate clinical management strategy for the prevention of caries ([Brunelle and Carlos, 1990](#)) ([Stephen, 1993](#)) ([Bartizek et al., 2001](#)) and to promote tooth remineralization and reduce demineralization ([Featherstone et al., 1990](#)) ([Chow, 1990](#)). Fluoride can be administered in many different forms, most commonly sodium fluoride (NaF), sodium monofluorophosphate (NaMFP) and stannous fluoride (SnF₂). However, besides the fluoride form and concentration, there are other aspects of a dentifrice that have an influence in the uptake of fluoride to enamel as has been shown in *in vitro* and *in situ* investigations ([Barlow et al., 2009](#), [Fowler et al., 2006](#), [Fowler et al., 2009](#)).

In vitro and *in situ* erosion models are the most commonly used methods to investigate the short-term performance of new dentifrice formulations indicated for dental erosion ([Shellis et al., 2011](#)). Currently, there is no validated clinical methodology or clinical index to monitor the progression of erosive tooth wear and enamel tissue loss ([Shellis et al., 2011](#)), and most of the devices used for detection of changes in mineral content can only be performed on specially prepared specimens ([Attin, 2006](#)). *In situ* dental erosion models involve the use of appliances or other devices in the human mouth that simulate the process ([Zero, 1995](#)) and they allow the effect of an erosive challenge to be evaluated under intra oral conditions but with some controlled experimental variables. *In situ* models are placed in between the continuum of *in vitro* models and clinical studies and can provide evidence of the potential effect of new therapies in inhibiting demineralization and promoting remineralization ([Zero, 1995](#)). However, the extrapolation of their result to clinically relevant evidence must be carefully considered.

In this study, an *in situ* dental erosion model will be used to investigate the efficacy of an experimental dentifrice in promoting the enamel remineralization of previously demineralized (eroded) bovine enamel. The experimental dentifrice will contain 1150ppm fluoride (as sodium fluoride [NaF]) and 5% w/w potassium nitrate [KNO₃], an ingredient with well-established efficacy at providing relief from dentinal hypersensitivity ([Schiff et al., 1994](#), [Gillam, 1996](#)). This study will employ as a reference control a marketed, dentifrice indicated for erosion and containing 1100 ppm fluoride as stannous fluoride, and a placebo dentifrice which will be similar to the experimental dentifrice but will contain 0ppm fluoride.

2.1 Study Rationale

This *in situ* study has been designed to evaluate the efficacy of an experimental dentifrice to remineralize previously demineralized (eroded) enamel over a 12 hour period. Existing clinical data supports the ability of sodium fluoride to remineralize enamel over a 4 hour period in this *in situ* model (see [Section 2.2](#)), however the specific combination of ingredients (actives and

excipients) in the experimental dentifrice have not been tested previously. Additionally, the intended claims associated with the experimental dentifrice require a test period of 12 hours which is longer than previously evaluated.

Whilst the experimental dentifrice will make claims on the suitability of the formulation to help mitigate against dentinal hypersensitivity (DH), the anti-DH performance of 5% KNO₃ is already well established (see [Section 2.2](#)). DH assessments are therefore not required.

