To investigate the efficacy of a marketed, reference dentifrice containing 1100ppm fluoride, to enhance remineralization, inhibit demineralization, to reduce future acid-induced demineralization and to promote fluoride uptake in enamel compared to a placebo dentifrice (0ppm fluoride) after 4 and 12 hours of intra-oral exposure.	%SMHR, %RER, EFU, ARR at 4 and 12 hrs.
Exploratory	
To calculate the proportion of subjects who evidence a RER ratio (%RER 0ppm fluoride placebo and 5% KNO ₃ : %RER experimental dentifrice containing 1150 ppm fluoride) ≥ 3 and ≥ 2.5	%RER at 4 and 12 hrs.
Safety	
To assess the oral tolerability of an experimental dentifrice containing 1150ppm fluoride and 5% KNO ₃ .	Treatment emergent adverse events

Abbreviations: SMHR: Surface micro hardness recovery, RER: Relative erosion resistance, EFU: Enamel fluoride uptake, ARR: Acid resistance ratio, KNO₃: potassium nitrate.

This study will be considered successful if the experimental dentifrice containing 1150ppm fluoride and 5% KNO₃ demonstrates a statistically significant enhancement of remineralization, as measured by %SMHR in comparison with the placebo dentifrice after 4 hours intraoral phase.

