12.3 Statistical Analyses

Additional details of the proposed statistical analysis will be documented in the statistical analysis plan (SAP), which will be written following finalization of the protocol and prior to study unblinding. This section is a summary of the planned statistical analyses of the most important endpoints including primary and secondary endpoints.

Statistical testing of all endpoints in this study will be conducted at a two-sided significance level of 0.05. A sequential testing strategy will be applied to preserve the overall type-1 error control for the respective sequential comparisons between the Experimental dentifrice and Placebo Control at 4 hours for the %SMHR (primary endpoint) and %RER (secondary endpoint). There will be no further adjustments for multiplicity.

All analyses of erosion parameters will be primarily based on the ITT population. If there is more than a 10% difference in the overall number of subjects included in the PP and ITT analyses, the PP analyses will also be performed as supportive analyses.

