12.3.1 Primary Analysis

The primary endpoint will be the %SMHR at 4 hours and the comparison between the Experimental dentifrice and Placebo Control.

The null and alternative hypotheses are:

- H0: there is no difference between the products.
- H1: there is a difference between the products.

For each replicate within each specimen (collected after 4 hours *in situ* remineralization) within a particular study visit, the %SMHR (at the replicate level) will be derived as $[(E1-R)/(E1-B)] * 100$

where:

B = indentation length (μm) of sound enamel at baseline

E1 = indentation length (μm) after first erosive challenge

R = indentation length (μm) after 4 hours *in situ* remineralization

Property of Haleon- Confidential

May not be used, divulged, published or otherwise disclosed without the consent of Haleon

The %SMHR at the subject visit level (to be used in the analysis) will be derived as the mean of the specimen means (across evaluable replicate %SMHR within a specimen) within that visit. Missing data or data deemed as non-evaluable by the laboratory will not be used in these derivations.

A mixed model (including results across all 3 study products) will be used to analyze the %SMHR at 4 hours with fixed effects for treatment and study visit, as well as random effect for subject. Kenward Rogers degrees of freedom approach will be applied. The least square means for each study product will be presented along with the differences between least square means (Experimental dentifrice - Placebo Control; including two-sided p-value and 95% confidence interval) to test for a difference between products.

The assumption of residual normality and variance homogeneity will be investigated from the mixed model through residual plots. If violated, a non-parametric method (Wilcoxon Signed Rank Test) will be performed for each pairwise comparison of interest as supportive analyses.

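### The plan ties its intended claims to a 12-hour test period, but its success criterion and error-controlled sequence cover only 4-hour tests, so every 12-hour result is an unprotected secondary.

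*Protocol*

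**What the plan says.** **Purpose.** Protocol 2.1 describes a study of the dentifrice's ability "to remineralize previously demineralized (eroded) enamel over a 12 hour period" and adds that "the intended claims associated with the experimental dentifrice require a test period of 12 hours which is longer than previously evaluated". It also says that sodium fluoride already has 4-hour support in this model, but that this particular combination of ingredients has not been tested.

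**Success.** The statement after Table 3-1 counts the study successful if the experimental dentifrice "demonstrates a statistically significant enhancement of remineralization, as measured by %SMHR in comparison with the placebo dentifrice after 4 hours intraoral phase". Section 12.3.1 agrees: "The primary endpoint will be the %SMHR at 4 hours and the comparison between the Experimental dentifrice and Placebo Control".

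**Error control.** Protocol 12.3 tests in sequence the Experimental dentifrice against "Placebo Control at 4 hours for the %SMHR (primary endpoint) and %RER (secondary endpoint"). SAP 4.4 plans the same. Both add: "There will be no further adjustments for multiplicity".

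**Contrary text.** The last paragraph of the Synopsis puts that sequence at the other time point: "Placebo Control at 12 hours for the %SMHR (primary endpoint) and %RER (secondary endpoint"). The Synopsis' own objectives table has the primary endpoint at 4 hours. The power statement (Protocol 12.1, SAP 1.4) is also labelled 12 hours, although its inputs are 4-hour results carried over by assumption.

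**12-hour tests.** Protocol 12.3.2 and SAP 4.4.2 plan three pairwise comparisons at 12 hours for each of %SMHR, %RER, ARR and EFU.

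**The concern.** The 12-hour time point is new to this model and is the one that Section 2.1 links to the claims. In the operative analysis text it enters neither the definition of success nor the protected sequence. Two consequences follow. The study can be declared successful with nothing shown at 12 hours. And a 12-hour statement would rest on a nominal p-value, with no rule fixed in advance for which 12-hour result has to be positive.

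Correcting the Synopsis to match the body does not cure this. It removes the only sentence that protects a 12-hour test.

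**Working it through.** **Inputs from Protocol 12.1.** n = 30 completers; two-sided 0.05; paired t-test. For %SMHR: difference 7.5, SD of differences 9.94 (higher value 12.16). For %RER: SD 17.5 with difference 10.7, or SD 20.3 with difference 12.4.

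**Assumed, not in the documents.** Correlations between endpoints from 0 to 0.9; EFU independent of the hardness measures; 12-hour effects and SDs equal to those at 4 hours. The protocol makes this last assumption for %SMHR; here it is extended to %RER.

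**1. The plan's power figure.** Noncentrality = (7.5/9.94) × √30 = 4.13 on 29 df, which gives power 97.9% (stated 97%). With SD 12.16, noncentrality is 3.38 and power 90.4% (stated 90%). The %RER settings give 89.9% and 89.8% (stated 90%). The figures reproduce. Because the inputs are 4-hour data, the same power applies to the 4-hour primary.

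**2. Success with no 12-hour effect.** The criterion uses only %SMHR at 4 hours, so its probability stays at about 98% whatever happens at 12 hours.

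**3. How many tests are protected.** 4 parameters × 3 pairs × 2 times = 24 comparisons. Two are protected, both at 4 hours. None of the 12 at 12 hours is.

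**4. False positives among 12-hour Experimental v Placebo tests, no effect present.**
- %SMHR and %RER: 1 − 0.95² = 9.75% if independent. Simulation of paired t-tests gives about 7–10% over correlations 0.9 to 0.
- All four parameters: the plan's formulas tie three of them together. (RER − SMHR)/100 = [(E1−E2) − (E1−R)]/(E1−B) = −(E2−R)/(E1−B), so ARR = 1 + (RER − SMHR)/100 when the same replicates are used. Simulating with this identity, the documents' SDs, SMHR–RER correlation 0 to 0.9 and EFU independent gives about 14–16%.
- For comparison, a single protected %SMHR test at 12 hours has error of at most 5%.

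**5. Power of a sequence that includes 12 hours.** The lower end is the product of single-test powers (correlation 0). The upper end is simulated at correlation 0.9.

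| Must all be significant | SDs 9.94 / 17.5 | SDs 12.16 / 20.3 |
|---|---|---|
| %SMHR 4 h, %RER 4 h (current plan) | 0.979 × 0.899 = 88%, up to 90% | 0.904 × 0.898 = 81%, up to 87% |
| %SMHR 4 h, %SMHR 12 h | 0.979² = 96%, up to 97% | 0.904² = 82%, up to 88% |
| %SMHR 4 h, %RER 4 h, %SMHR 12 h | 0.979² × 0.899 = 86%, up to 90% | 0.904² × 0.898 = 73%, up to 85% |

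The third row is the power to reach %SMHR at 12 hours when it follows both existing steps. Every step is tested at 0.05 only after the previous one passes, so family-wise error stays at 0.05.

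**The case against.** **The 4-hour primary has its own reason.** Section 2.1 gives the untested formulation first and the 12-hour need as an addition, and Section 12.1 says there are no historical 12-hour results. A primary at the time point with known effect and variability is sound. This stands, and the 4-hour primary should stay.

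**Section 2.1 asks for a test period, not for a protected test.** The 12-hour data are collected and tested under a prespecified model, and the absence of further adjustment is stated openly. The documents do not give the wording of the claims or the evidence they require. This stands in part: a reader might infer that the study yields no 12-hour evidence, and that is not so. What is missing is error control and a rule linking the 12-hour result to a claim.

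**The Synopsis protects 12 hours.** It does, and the power text also names 12 hours. So the protocol does not uniformly stop at 4 hours. But both objectives tables, the success statement, Protocol 12.3 and 12.3.1, and SAP 4.4 and 4.4.1 all point to 4 hours. Even on the Synopsis reading, success still depends on 4 hours alone.

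**The error rate is small for a claim resting on one test.** If the sponsor meant only %SMHR at 12 hours against placebo, its nominal error is 5%. The plan does not say so. In the other direction, a reader might compute 1 − 0.95⁴ = 18.5% for the four parameters. That figure needs four independent tests, which the ARR identity rules out.

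**Conclusion.** The point holds in this form: on the operative text, the time point that Section 2.1 ties to the intended claims has no error-controlled test and no place in the success criterion. If there is no 12-hour effect, the study still succeeds about 98% of the time under its own 4-hour assumptions. At least one false 12-hour Experimental v Placebo result then arises about 7–10% of the time for %SMHR and %RER, or about 14–16% across all four parameters.

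The 98% depends on the plan's difference of 7.5 and SD of 9.94. The error rates rest on assumed correlations and on an independent EFU. All figures use the paired t-test of the sample-size section, not the planned mixed model. The 4-hour primary analysis is unaffected. The change should be made before unblinding.

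**What to change.** 1. Bring the Synopsis testing paragraph and the time point in Protocol 12.1 and SAP 1.4 into line with the 4-hour primary.
2. In the same edit, extend the fixed sequence in Protocol 12.3 and SAP 4.4 with Experimental v Placebo %SMHR at 12 hours and then %RER at 12 hours, each tested at 0.05 only if the preceding step is significant.
3. After Table 3-1, state that a confirmatory 12-hour claim requires the %SMHR 12-hour step to be met, and that otherwise 12-hour results are supportive only.

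**The order is the sponsor's choice.** Appending the new steps after the two existing ones leaves the power of those two unchanged and gives 86–90% power to reach %SMHR at 12 hours (73–85% at the higher SDs). If %RER at 4 hours fails, the 12-hour results stay nominal, as they are now. Placing %SMHR at 12 hours directly after %SMHR at 4 hours gives 96–97% (82–88%), but %RER at 4 hours then loses its protection whenever the 12-hour step fails.

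**Cost.** Wording in two documents. No further subjects or data are needed, and the family-wise error stays at 0.05. If the sponsor does not want a confirmatory 12-hour claim, the minimum is one sentence stating that all 12-hour results are supportive.
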